8.1.2 Secondary study parameters/endpoints

- Feasibility / Adherence to the ketogenic diet
 - o Self-reported adherence, measured via in-house used questionnaire “Ketodieet”. Questionnaire has not validated but partly based on “Vragenlijst Intensive Monitoring Lareb (65)”, measures the amount of days subjects did not use the ketogenic diet. Serves as a tool during outpatient clinic visits to the dietician.
 - o Ketone levels in urine, self-measured thrice weekly by urine strips (Siemens, Multi stix 10SG)
 - o Ketone levels, measured at physical meetings with dietician, by Ketosemeter CareSense Dual
- Side effects & burden of diet, measured via in-house used questionnaire “Ketodieet”. Questionnaire has not validated but partly based on “Vragenlijst Intensive Monitoring Lareb (65)”, measures possible side effects mentioned by subjects during the use of the ketogenic diet. Serves as a tool during outpatient clinic visits to the dietician.
- Results of the prediction model/chance assessment tool (30), providing the estimated chance (%) of HCA regression to 0,5 cm at 1 and 2 years after diagnosis.
- Change in Liver fat content, measured on MRI
- Change in plasma parameters:
Fasting glucose, fasting insulin, HbA1c, total cholesterol, HDL-cholesterol, LDL-cholesterol, free fatty acids, triglycerides levels, branched amino acids, IGF -1, Growth hormone (hGH), β -Hydroxybutyrate
- Quality of life measured by RAND-36 (66-69), Dutch version 2, 2012. Higher score meaning higher QoL
- Change in body weight (kg)
- Change in body composition (fat mass / fat free mass)
 - o via Bio-electrical Impedance Analysis (Bodystat quadscan 4000, Euromedix, Leuven, Belgium)
- Resting Energy Expenditure
 - o Via Quark RMR, Cosmed Benelux B.V., Nieuwegein, The Netherlands

8.1.3 Other study parameters

- Baseline subject characteristics such as age, sex, weight, length, BMI, oral contraceptive use, other medication use, comorbidities, size of hepatocellular adenoma at baseline, multiple or single lesion, amount of hepatocellular adenoma's at baseline, subtype of hepatocellular adenoma, time since initial diagnosis, time since last imaging study, imaging study provided (MRI/CT/Ultrasound), referring hospital and active pregnancy wish.
- Macronutrient intake (3-day food diary)
- Physical activity by IPAQ questionnaire (70, 71), Dutch version 1, 23-01-2011. Higher score means a higher level of physical activity
- Incidence of symptomatic HCA, defined as:
 - o HCA rupture/bleeding confirmed on CT / MRI
 - o for which admittance into the hospital or (endovascular) treatment is indicated.

8.2 Randomisation, blinding and treatment allocation

All subjects in our study will be allocated to the dietary intervention and henceforth cannot be blinded.

8.3 Study procedures

Standard procedure / current best clinical practice

Main study population

Subjects present themselves at our outpatient clinic after referral from a peripheral or other tertiary/university hospital. Subjects will be receiving additional imaging studies (f.i. an MRI) if the necessary imaging study has not been conducted at the peripheral/referring hospital, according to current standard protocol/clinical practice. Afterwards their case will be discussed in our multidisciplinary meeting, including a (liver) radiologist, hepatobiliary surgeon, gastroenterologist / hepatologist and dietician.

During current clinical practice, subjects will enter the "Wait and See" / "Active Surveillance" period for 6 months (30) based on several criteria. See figure 1 for the management flowchart.

Subpopulation

Subjects eligible for inclusion into the study subpopulation are already being treated via the outpatient clinic via active surveillance. After the initial 6 months of active surveillance (with advice consisting of cessation of use of oral contraceptives and aiming for weight loss), subjects have been subjected to an MRI. If this MRI shows no or only a minimal (5mm) reduction of the size of the HCA, patients are subjected to another active surveillance period of 6 months after which another MRI is performed. We want to provide the patients with the option to adhere to the ketogenic diet as a potential therapeutic option.

Intervention / Study procedure

Time of inclusion:

Eligible subjects visiting the outpatient clinic after discussion of their case in the multidisciplinary meeting are invited to participate in the study. The possible participant is asked whether she wants to be approached for further information on this study. The gastro-enterologist / hepato-biliary surgeon shortly explains the purpose of the study after which, if the subject agrees to it, the study investigator explains the study design and purpose in more detail. Subjects receive written information and are offered a reflection period of one week before they are contacted again about participation in the study. In case informed consent is given, subjects will receive an appointment with a dietician.

Follow-up and outpatient visits will be identical to normal procedure, except the extra appointments with the dietician and the additional blood samples drawn by venous puncture on T₀, T₃ and T₅.

Consultation by Dietician

This consult will focus on explaining the study diet, nutritional assessment, adherence to the diet, measurements, advice and instruction in case of possible side effects.

Nutritional assessment

Nutritional assessment will take place during the study visits at the outpatient clinic and consists of:

- Resting energy expenditure (Indirect calorimetry)
- Body composition by bioelectrical impedance analysis (BIA)
- 3-day food diary filled in at home and cross checked during the study visits.
- Anthropometric measurements, body weight will be measured during visits to the outpatient clinic.

Nutritional assessment is part of standard dietetic care. For the operational procedures we refer to the NAP website (72). The procedure involves measurement of inspired and expired air. Participants are asked to lay down in a supine position for approximately half an hour and to breath in and out of a ventilated hood. Bio impedance involves the patient to lay down in a supine position or stand on a special scale with special handgrips for 1 minute.

Questionnaires

Questionnaires will focus on adherence and any possible side effects / symptoms subjects might experience during the ketogenic diet. Other questionnaires conducted during study focus on quality of life and physical activity.

Consultation by Clinician / Investigator

This consult will focus on any possible abdominal pain / complaints, any complaints after halting oral contraceptives, advice to currently avoid pregnancy and advice concerning when to contact our outpatient clinic.

Imaging studies

Subjects will receive their follow-up MRI according to normal treatment protocol after 6 months. No additional imaging studies will be performed for this study, extra measurements will be made on already acquired imaging studies to calculate the liver fat content.

Laboratory testing

Blood will be acquired by venous puncture for measuring fasting parameters. Blood sampling will be done thrice, each time 2 tubes of 10ml will be withdrawn.

Urine testing

Ketones / Acetoacetate in urine will be assessed thrice weekly by subjects themselves using a simple urinestrip to determine / confirm ketose state and therefore adherence. Subjects will be carefully instructed during their clinical appointments on how to use these strips.

Followup overview:

Table 2: Study overview, window for appointments: T₁&T₂: +/- 3 days, T₃-T₅: +/- 1 week

Procedure	T ₀ Baseline	T ₁ 2 weeks	T ₂ 6 weeks	T ₃ 3 months	T ₄ 4 months	T ₅ 6 months
Dietary restriction	Start diet (Phase 1)			Start diet (Phase 2)		End of diet
Informed Consent	X					
Type of contact	Physical	Telephone	Telephone	Physical	Telephone	Physical
Consultation by Dietician	Outpatient clinic	By phone	By phone	Outpatient clinic	By phone	Outpatient clinic
Consultation by Clinician / investigator	Outpatient clinic					Outpatient clinic
MRI-Followup						X
Laboratory testing	X			X		X
Anthropometric measurements	X			X		X
Nutritional assessment:	X			X		X
Questionnaires:						
IPAQ:	X			X		X
Rand-36:	X			X		X
Food Diary:	X	X	X	X	X	X
Side effects:		X	X	X	X	X

8.4 Withdrawal of individual subjects

Subjects can leave the study at any time for any reason if they wish to do so without any consequences. The investigator can decide to withdraw a subject from the study for urgent medical reasons.

8.4.1 Specific criteria for withdrawal

Inclusion takes place prior to starting the diet. When subjects develop severe symptoms of their hepatocellular adenoma, f.i. haemorrhage, they will be withdrawn from the study and they will be treated according to the current best clinical practice, f.i. by trans-arterial embolization. Severe symptoms are defined as symptoms for which hospital admittance is indicated / invasive treatment is indicated. Subjects will also be withdrawn from the study if they become pregnant.

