8.5 Replacement of individual subjects after withdrawal

When a subject is withdrawn from the study before starting the ketogenic diet or if they opt out themselves for any reason, a new subject will be included in our study.

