8.6 Follow-up of subjects withdrawn from treatment

Subjects will be still be included in follow-up if they did not complete their dietary intervention.

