9.4 Follow-up of adverse events

All AEs will be followed until they have abated, or until a stable situation has been reached. Depending on the event, follow up may require additional tests or medical procedures as indicated, and/or referral to the general physician or a medical specialist. SAEs need to be reported till end of study within the Netherlands, as defined in the protocol.

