10. STATISTICAL ANALYSIS

Categorical data will be presented as numbers (percentage) and continuous variables as mean (standard deviation/normal distribution) or median (interquartile range/no normal distribution).

An Intention-to-treat analysis will be conducted to account for the feasibility of the caloric restricted and ketogenic diet. A two-sided significance level of 0.05 will be used for all primary and secondary analyses unless stated otherwise.

Statistics will be computed using IBM SPSS software version 21.0 (Chicago, IL) or R version 4.0.2 or newer.

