10.1 Primary study parameter

The primary endpoint is the reduction in size (in cm) of the largest diameter of the largest hepatocellular adenoma after 6 months, compared to our matched historical controls. A multivariable linear regression model will be used to estimate the difference in tumour regression between the treatment group and the historical control group. The model will be adjusted for age, change in body weight, the ketogenic diet and oral contraceptive use at baseline.

Subpopulation: the same model will be constructed but will not be adjusted for oral contraceptive use at baseline.

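### Section 8.4.1 withdraws women with severe adenoma symptoms, and women who become pregnant, from the study and not only from the diet, which does not fit an intention-to-treat analysis of the month-6 diameter and leaves their follow-up under 8.6 unclear

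*Protocol*

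**What the plan says.** Section 8.4.1 of the protocol: "When subjects develop severe symptoms of their hepatocellular adenoma, f.i. haemorrhage, they will be withdrawn from the study". The trigger is then defined: "Severe symptoms are defined as symptoms for which hospital admittance is indicated / invasive treatment is indicated". Pregnancy is a further ground for withdrawal from the study in the same section.

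Section 8.6, whose heading speaks of withdrawal from treatment, says: "Subjects will be still be included in follow-up if they did not complete their dietary intervention". It makes no exception for the women in 8.4.1.

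Section 8.5 provides a replacement in two cases: "When a subject is withdrawn from the study before starting the ketogenic diet or if they opt out themselves for any reason". A woman withdrawn by the investigator for severe symptoms during the diet is in neither.

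Section 10: "An Intention-to-treat analysis will be conducted to account for the feasibility of the caloric restricted and ketogenic diet". Section 10.1: "The primary endpoint is the reduction in size (in cm) of the largest diameter of the largest hepatocellular adenoma after 6 months", compared with matched historical controls. Under 8.1.1 the second measurement is at T5, six months after the start of the diet. The study overview in 8.3 shows one follow-up MRI, at T5, and the text there describes it as routine care: "Subjects will receive their follow-up MRI according to normal treatment protocol after 6 months".

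The protocol does not say that the data of withdrawn women are deleted, nor how their month-6 diameter is obtained or handled.

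**The concern.** Intention-to-treat on a month-6 measurement needs that measurement, or a planned substitute, for every woman who started. Section 8.4.1 ends study participation, and for symptomatic women it does so because of how the adenoma behaves. From then on the study requires no T5 diameter from them. Whether the outcome is missing then depends on the tumour, which is the kind of missingness that intention-to-treat is meant to avoid.

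If 8.6 is taken to keep these women in follow-up, a second problem appears. Section 8.4.1 itself names embolisation as a possible treatment. A diameter measured after embolisation or resection may describe the procedure more than the diet, and section 10.1 does not separate the two.

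The comparison is with historical controls and not with a concurrent randomised group. Any difference in how such women are handled in the two cohorts therefore passes directly into the estimated effect.

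**Working it through.** **1. One case, read against each section.** Take a woman admitted for a bleed in month 2.
- 8.4.1: she is withdrawn from the study, so no T5 diameter is required.
- 8.6: she did not complete the diet, so she stays in follow-up.
- 8.5: she had started the diet and did not opt out herself, so she is not replaced.
- 10 and 10.1: she belongs to the intention-to-treat population and needs a month-6 diameter.

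8.4.1 and 8.6 can both stand if withdrawal from the study and withdrawal from treatment are kept strictly apart. The text does not say which applies to her, and each gives different data for the primary endpoint. On the first, the promise in section 10 has no measurement behind it.

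**2. The plan's sample size (4.4).** The target is 20% of 65 mm = 13 mm. No SD is stated. From the month-6 IQR (56 to 80 mm), assuming normality, SD = (80 − 56)/1.349 = 17.8 mm. Per group, n = 2 × [17.8 × (1.960 + 1.645)/13]², which rounds up to 49. The t-based calculation gives 50, and dividing the normal formula by the Wilcoxon efficiency of 0.955 gives 51. The stated 51 is thus reproduced, read as a number per group. With the same SD, power is 0.969 at 55 per group and 0.955 at 50. Losing five women costs little power, so the issue is bias.

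**3. Shift in the diet mean if such women drop out.** If k of 55 women are lost and their regression would have been D mm less than that of the rest, the mean without them is too high by (k/55) × D. The documents give neither k nor D, so both are assumptions:
- k = 1, 2, 3 or 5.
- D = 10 mm, a moderate deficit.
- D = 17 mm, the historical fall in the median (82 − 65).
- D = 30 mm, no regression at all where the others average 17 + 13 = 30 mm.

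| Women lost | D = 10 mm | D = 17 mm | D = 30 mm |
|---|---|---|---|
| 1 of 55 | 0.18 | 0.31 | 0.55 |
| 2 of 55 | 0.36 | 0.62 | 1.09 |
| 3 of 55 | 0.55 | 0.93 | 1.64 |
| 5 of 55 | 0.91 | 1.55 | 2.73 |

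The shift is 0.18 to 2.73 mm. Against the target that is 0.18/13 = 1.4% to 2.73/13 = 21%.

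**4. Shift if post-procedure diameters are counted.** Suppose three women have the lesion resected and each is scored as an 82 mm reduction. Compared with the 30 mm average, the mean rises by 3 × (82 − 30)/55 = 2.8 mm. Compared with no regression, it rises by 3 × 82/55 = 4.5 mm. This is illustrative only: 82 mm is the historical median at baseline, the trial admits adenomas of any size (4.1), and the protocol does not say that a resected lesion would be scored this way.

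**5. The contrast.** Sections 3 and 4 concern the diet group alone. In the comparison, the bias from dropping women is (share lost × D) in the diet group minus the same product in the controls. The protocol does not say how controls who bled or were treated were handled, so the second term is unknown.

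**The case against.** The strongest reply is that this is a small ambiguity. Section 8.6 concerns leaving treatment and 8.4.1 leaving the study, so there is no literal contradiction. The month-6 MRI is routine care and may exist anyway. Handling of missing or post-procedure diameters is commonly left to the statistical analysis plan, which is not at hand. Much of this stands, and it limits the point. What remains is the collection rule: an analysis plan can choose a method for missing values, but it cannot restore follow-up that the protocol has ended.

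A reader might also infer more than the text supports:
- **That every woman whose adenoma bleeds is withdrawn.** The rule is limited to symptoms that indicate admission or invasive treatment.
- **That 9.4 conflicts with 8.4.1.** "All AEs will be followed until they have abated, or until a stable situation has been reached" is safety follow-up, and it can continue after a woman leaves the study.
- **That bleeds are lost from the survival analysis in 10.3.** The bleed that triggers withdrawal has already occurred and is counted.
- **That the worst tumour outcomes are removed from the primary result.** No section says that data are deleted, and a severe bleed is not the same as a poor change in diameter.
- **That the bias must favour the diet.** The direction also depends on how such women were handled in the historical cohort, which is not stated.
- **That the 27.2% haemorrhage frequency in section 1 gives the expected loss.** It is not a six-month rate under surveillance.

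**Conclusion.** The point holds as a mismatch between the withdrawal rule and the analysis that the protocol promises. Followed as written, 8.4.1 leaves symptomatic women without a study-mandated T5 diameter for a reason tied to the adenoma, and does the same for women who become pregnant. Whether 8.6 brings them back is unclear, and if it does, a diameter after an invasive procedure may be credited to the diet.

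On assumed losses of 1 to 5 of 55 women with 10 to 30 mm less regression, the diet mean shifts by about 0.2 to 2.7 mm, or 1% to 21% of the 13 mm target. Both inputs are assumptions, and the effect on the contrast with controls cannot be derived from the documents. The sample size is unaffected. The problem would not by itself overturn a 13 mm effect, but it should be corrected because it is cheap to prevent and cannot be repaired once follow-up has stopped.

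**What to change.** Reconcile 8.4.1 with 8.6 and section 10:
- State that the events in 8.4.1 may end the diet but do not end data collection. Only withdrawn consent does that. Leave the clinical care described in 8.4.1 as it is.
- Collect outcome data to month 6 from routine records and routine imaging, and keep these women in the primary intention-to-treat population.
- State in 10.1 that a diameter measured after an invasive procedure does not count as regression on the diet. Handle such women the same way in the historical controls, as far as the control data allow.
- Add sensitivity analyses, for example one that assumes no regression and one that excludes these women. The first uses the last diameter before the event. With no study MRI between baseline and T5 this will usually be the baseline value, so it suits a sensitivity analysis better than the primary one.

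**Cost:** a wording amendment to 8.4.1, 8.6 and 10.1, and a little record review. No extra visits or scans are needed. The historical cohort is retrospective and may lack event dates or pre-event diameters, so matching the rule there may be only partly possible. The estimate may become slightly less favourable to the diet.

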8.5 Replacement of individual subjects after withdrawal

When a subject is withdrawn from the study before starting the ketogenic diet or if they opt out themselves for any reason, a new subject will be included in our study.

8.6 Follow-up of subjects withdrawn from treatment

Subjects will be still be included in follow-up if they did not complete their dietary intervention.

8.7 Premature termination of the study

There are no projected risks to the safety and feasibility of this trial, see chapter 13. Therefore, no criteria for premature termination were formed.

9. SAFETY REPORTING

9.1 Temporary halt for reasons of subject safety

In accordance to section 10, subsection 4, of the WMO, the sponsor, investigator or principal investigator will suspend the study if there is sufficient ground that continuation of the study will jeopardise subject health or safety. The sponsor will notify the accredited METC without undue delay of a temporary halt including the reason for such an action. The study will be suspended pending a further positive decision by the accredited METC. The investigator will take care that all subjects are kept informed.

9.2 AEs, SAEs and SUSARs

9.2.1 Adverse events (AEs)

Adverse events are defined as any undesirable experience occurring to a subject during the study, whether or not considered related to ketogenic diet. All adverse events reported spontaneously by the subject or observed by the investigator or his staff will be recorded. When adverse or serious adverse events are observed, the principal investigator will be informed. Subsequently, the principal investigator takes responsibility for the correct processing of the events.

Known minor side effects of the ketogenic diets (constipation, diarrhoea, nausea and/or vomiting) will be analysed separately and are therefore not considered an adverse effect.

9.2.2 Serious adverse events (SAEs)

A serious adverse event is any untoward medical occurrence or effect that

- results in death;
- is life threatening (at the time of the event);
- requires hospitalisation or prolongation of existing inpatients' hospitalisation;
- results in persistent or significant disability or incapacity;
- is a congenital anomaly or birth defect
- any other important medical event that did not result in any of the outcomes listed above due to medical or surgical intervention but could have been based upon appropriate judgement by the investigator.

An elective hospital admission will not be considered as a serious adverse event.

The investigator will report all SAEs to the sponsor without undue delay after obtaining knowledge of the events.

The sponsor will report the SAEs through the web portal *ToetsingOnline* to the accredited METC that approved the protocol, within 7 days of first knowledge for SAEs that result in death or are life threatening followed by a period of maximum of 8 days to complete the initial preliminary report. All other SAEs will be reported within a period of maximum 15 days after the sponsor has first knowledge of the serious adverse events.

9.2.3 Suspected unexpected serious adverse reactions (SUSARs)

Not applicable since this study does not involve an investigational medicinal product.

9.3 Annual safety report

Not applicable since this study does not involve an investigational medicinal product.

9.4 Follow-up of adverse events

All AEs will be followed until they have abated, or until a stable situation has been reached. Depending on the event, follow up may require additional tests or medical procedures as indicated, and/or referral to the general physician or a medical specialist. SAEs need to be reported till end of study within the Netherlands, as defined in the protocol.

